### **13.3. Recording Adverse Events**

Adverse events spontaneously reported by the patient and/or in response to an open question from the study personnel or revealed by observation will be recorded during the study at the investigational site. Information about AEs will be collected from the time of vector infusion until the end of the study. Serious Adverse Event information will be collected from signing of consent form until the last study visit. The AE term should be reported in standard medical terminology when possible. For each AE, the Investigator will evaluate and report the onset (date (and time if during Visit 2)), resolution (date (and time if start date during Visit 2)), intensity, causality, action taken, serious outcome (if applicable), and whether or not it caused the patient to discontinue the study.

It is important to distinguish between serious and severe AEs. Severity is a measure of intensity whereas seriousness is defined by the criteria under [Section 13.1.1.2](#). An AE of severe intensity may not be considered serious.

### **13.4. Reporting Adverse Events**

All SAEs (related and unrelated) will be recorded from signing of consent form until the last study visit. Any SAEs considered possibly or probably related to the investigational product and discovered by the Investigator at any time after the study should be reported. All SAEs must be reported to AveXis or designee within 24 hours of the first awareness of the event. The Investigator must complete, sign and date the SAE pages, verify the accuracy of the information recorded on the SAE pages with the corresponding source documents, and send a copy by fax or e-mail to AveXis or designee.

Additional follow-up information, if required or available, should all be faxed or e-mailed to AveXis or designee within 24 hours of receipt and this should be completed on a follow-up SAE form and placed with the original SAE information and kept with the appropriate section of the eCRF and/or study file.

AveXis is responsible for notifying the relevant regulatory authorities of certain events. It is the Principal Investigator's responsibility to notify the IRB or IEC of all SAEs that occur at his or her site. Investigators will also be notified of all unexpected, serious, product-related events (7/15 Day Safety Reports) that occur during the clinical study. Each site is responsible for notifying its IRB or IEC of these additional SAEs.

## 14. STATISTICS

This section summarizes key aspects of the analysis plan including definitions of co-primary, co-secondary, and [REDACTED] and safety endpoints, and the methods to be used to test the primary effectiveness hypothesis. Additional details regarding methods for the final data analysis will be provided in a separate Statistical Analysis Plan (SAP) which will be finalized and submitted to the Investigational New Drug application prior to the enrollment of the first patient. The SAP will detail all analyses and data displays and will be executed according to Standard Operating Procedures in a controlled environment.

### 14.1. Study Endpoints and Populations

#### 14.1.1. Study Endpoints

The primary and efficacy endpoint will be compared to the null. The survival co-primary efficacy variable will be evaluated relative to literature-based historical controls (such as the Pediatric Neuromuscular Clinical Research Network [PNCr] [21]). These were selected on the basis of comparability to the target population and similarity to the investigational device.

##### 14.1.1.1. Co-Primary Efficacy Endpoint

The co-primary efficacy endpoints are:

- The proportion of patients that achieve functional independent sitting for at least 30 seconds at the 18 months of age study visit. It is defined by the Bayley Scales of Infant and Toddler Development (Version 3) ([Appendix 2](#)), confirmed by video recording, as a patient who sits up straight with the head erect for at least 30 seconds.
- The survival at 14 months of age. Survival is defined by the avoidance of the combined endpoint of either (a) death or (b) permanent ventilation, which is defined by tracheostomy or by the requirement of  $\geq 16$  hours of respiratory assistance per day (via non-invasive ventilatory support) for  $\geq 14$  consecutive days in the absence of an acute reversible illness, excluding perioperative ventilation. Permanent ventilation, so defined, is considered a surrogate for death.

An “acute reversible illness” is defined as any condition other than SMA that results in increased medical intervention (e.g., increased requirement for respiratory support; use of other concomitant medications as rescue) requirements and is expected to be reversible or improved following definitive intervention (e.g., surgery, antibiotics) or introduction of escalated supportive care, such as hospitalization (e.g., for upper respiratory infection, spontaneous fracture). The specific duration of the condition antecedent intervention shall not be considered in the definition of “acute.” The date of “definitive intervention” shall be defined as the date of provision of a procedure (e.g., surgery, etc.) or medication (e.g., antibiotics) intended to cure or substantially improve the condition. For conditions such as viral respiratory infections for which supportive care is provided, the date of “definitive intervention” shall be considered the date of hospitalization or substantial escalation of care.

█ [REDACTED]  
█ [REDACTED]  
█ [REDACTED]  
█ [REDACTED]  
█ [REDACTED]  
█ [REDACTED]  
█ [REDACTED]

#### 14.1.1.4. Safety Endpoints

Assessment of the safety and tolerability of AVXS-101 treatment, including:

- Incidence of elevated LFTs and/or unresolved LFEs
- Incidence of CTCAE Grade 3 or higher toxicity, treatment-emergent adverse events
- Clinically significant changes in laboratory values, physical exams, cardiac assessments or vital signs
- Research Immunology Blood Labs including serum antibody to AAV9 and SMN as well as IFN- $\gamma$  ELISpot to detect T cell responses to AAV9 and SMN

#### 14.1.2. Statistical Analysis Populations

##### 14.1.2.1. Intent-to-Treat Population (ITT)

The ITT population will consist of symptomatic patients with biallelic- deletion mutations of *SMN1* (exon 7/8 common homozygous deletions) and 2 copies of *SMN2* without the known gene modifier mutation (c.859G>C) who receive an IV infusion of AVXS-101 at < 180 days of age. The first 3 patients enrolled must meet the criteria for the Intent-to-Treat Population.

##### 14.1.2.2. Efficacy Completers Population

The efficacy completers analysis population will consist of:

- All treated patients who reach 14 months of age for the survival endpoint or 18 months of age for the endpoint of achievement of functional independent sitting, OR
- All treated patients who meet discontinuation criteria, discontinue the study due to an AE or experience death

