### **8.3. Patient Withdrawal Criteria**

Patients may be discontinued from the study for the following reasons:

- Death
  - An autopsy will be requested for any patient who expires following participation in a gene replacement study [25] (see Autopsy Plan in [Appendix 1](#))
- Failure to comply with protocol-required visits or study procedures for 3 or more consecutive visits that are not rescheduled, unless due to hospitalization
- Parent(s)/legal guardian(s) withdraws consent
- Investigator discretion

Early termination procedures should be completed within 14 days for any patient who prematurely discontinues the study for any reason, as indicated in [Appendix 5](#).

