##### 14.1.2.3. All Enrolled Population

The all enrolled population will consist of all patients who receive an IV infusion of AVXS-101. Analyses of endpoints in this population are considered descriptive.

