### 14.2. Sample Size Calculation

This is a pivotal Phase 3, open-label, single-arm, single-dose, study assessing the efficacy and safety of AVXS-101 (gene replacement therapy) in up to twenty (20) patients with spinal muscular atrophy (SMA) Type 1 who meet enrollment criteria, may be either symptomatic or pre-symptomatic and are genetically defined by no functional survival motor neuron 1 gene (*SMN1*) with 1 or 2 copies of survival motor neuron 2 gene (*SMN2*) and who are < 6 months (< 180 days) of age **at the time** of gene replacement therapy (Day 1). Enrolling up to twenty (20) patients under the broader enrollment criteria is projected to enable enrollment of at least 15 patients that meet the Intent-to-Treat Population (ITT) criteria. The ITT population is identified as symptomatic patients with bi-allelic *SMN1* deletions and 2 copies of *SMN2* without the *SMN2* gene modifier mutation (c.859G>C) and will comprise the primary population for evaluation of the primary and secondary endpoints. Study power is based upon efficacy analysis of the ITT population. Furthermore, the first 3 patients enrolled must meet criteria for the Intent-To-Treat Population to enable a comparison of CHOP-INTEND scores at 1-month following gene replacement therapy to enable a comparison of patient response between AVXS-101-CL-303 patients and Cohort 2 patient results from the Phase 1 trial (AVXS-101-CL-101). Patients with 1 copy of *SMN2*, pre-symptomatic patients and patients with the *SMN2* gene modifier mutation (c.859G>C) and other permutations outside of those specified in the ITT population will be evaluated separately as part of additional subgroup analyses. Details of all analyses will be contained within the Statistical Analysis Plan.

The 2 co-primary efficacy endpoints will be assessed in sequence: The endpoint of functional independent sitting will be assessed first and, only if this assessment meets statistical significance will the endpoint of survival be assessed.

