#### 14.3.2. Primary and Secondary Efficacy Analysis

Primary and secondary efficacy analyses will be based on the ITT population, those patients that are symptomatic with biallelic- deletion mutations of *SMN1* and 2 copies of *SMN2* without the *SMN2* gene modifier mutation (c.859G>C). These analyses are to test the superiority of AVXS-101 to the results from natural observation study (PNCR) [21].

The first co-primary efficacy hypothesis to be tested is:

$$\begin{aligned} \mathbf{H}_0: p_{AVXS-101} &= 0.1\% \\ &\textit{versus the alternative} \\ \mathbf{H}_a: p_{AVXS-101} &> 0.1\%, \end{aligned}$$

where  $p$  is the proportion of functional independent sitting for at least 30 seconds at the 18 months of age study visit.

The second co-primary efficacy hypothesis to be tested is:

$$\begin{aligned} \mathbf{H}_0: p_{AVXS-101} &= p_{HISTORICAL-FINKEL} \\ &\textit{versus the alternative} \\ \mathbf{H}_a: p_{AVXS-101} &\neq p_{HISTORICAL-FINKEL}, \end{aligned}$$

where  $p$  is the proportion surviving at 14 months of age.

Primary efficacy endpoints will be examined on the ITT population. Testing for the first co-primary endpoint, functional independent sitting will first be performed using 1-sided exact binomial test. Only if the null hypothesis of equality in proportion of functional independent sitting is rejected at  $p < 0.025$ , will the co-primary endpoint survival improvement be tested using 2-sided Fisher's Exact test on the ITT population, comparing to matched patients from natural observational study (PNCR). This hierarchy approach strongly protects the Type I error rate.

The hypothesis for both co-secondary efficacy endpoints to be tested is:

$$\begin{aligned} \mathbf{H}_0: p_{AVXS-101} &= 0.1\% \\ &\textit{versus the alternative} \\ \mathbf{H}_a: p_{AVXS-101} &> 0.1\%, \end{aligned}$$

where  $p$  is the proportion of patients maintaining the ability to thrive/are independent of ventilatory support.

One-sided exact binomial tests will be executed for secondary efficacy analyses on the ITT population.

A sensitivity analysis will be conducted by repeating the primary efficacy analysis on the efficacy completers analysis population.

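### The Efficacy Completers set is not limited to ITT patients, so the stated sensitivity analysis repeats the co-primary tests on what is in practice the All Enrolled population

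*Protocol*

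**What the plan says.** Section 14.1.2.2 defines Efficacy Completers by two limbs joined by OR. The first, which ends by naming the sitting milestone, is "All treated patients who reach 14 months of age for the survival endpoint or 18 months of age for the endpoint of achievement of functional" (cut short here). The second is "All treated patients who meet discontinuation criteria, discontinue the study due to an AE or experience death". Neither limb mentions ITT membership, SMN1 mutation type, SMN2 copy number, the c.859G>C modifier or symptom status.

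The discontinuation reasons in section 8.3 are death, "Failure to comply with protocol-required visits or study procedures for 3 or more consecutive visits that are not rescheduled", "Parent(s)/legal guardian(s) withdraws consent" and investigator discretion.

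The ITT population (section 14.1.2.1) is narrower than the enrolled population. It takes symptomatic infants with bi-allelic SMN1 deletions and two SMN2 copies without the modifier, dosed before 180 days of age. Sections 7.1 and 8.1 also admit pre-symptomatic infants, point mutations, one SMN2 copy and modifier carriers.

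On use of the populations:
- Section 14.3.1 runs the co-primary and co-secondary analyses on both ITT and Efficacy Completers, with ITT primary.
- Section 14.3.2 adds: "A sensitivity analysis will be conducted by repeating the primary efficacy analysis on the efficacy completers analysis population".
- Section 14.1.2.3 says of all infused patients: "Analyses of endpoints in this population are considered descriptive".
- Section 14.2 says that one-copy, pre-symptomatic and modifier patients, and other permutations outside ITT, "will be evaluated separately as part of additional subgroup analyses".

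**The concern.** A completers analysis placed beside an ITT analysis is expected to show whether the result depends on patients who left early. This one cannot. The second limb keeps nearly everyone who leaves, and the same observed-data rule in section 14.3.1 covers both sets. What remains different between the two analyses is that up to five patients outside ITT are added.

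Those patients are the ones that section 14.2 sets aside. The Synopsis (Statistical Methods) argues the 0.1% sitting null only for two SMN2 copies without the modifier. If the sensitivity result differs from the ITT result, the likely reason is case mix and not dropout. If it agrees, it says little about missing data. In a pivotal single-arm trial with about 15 ITT patients, readers will give weight to a supportive analysis, and this one could falsely reassure or falsely undermine.

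**Working it through.** **1. The plan's own power figures reproduce.** Inputs from section 14.2: 15 ITT patients less about 30% leaves 10 or 11; null sitting rate 0.1%; one-sided alpha 0.025; assumed sitting rate 30% to 40%; survival 80% against 25% in 26 controls, two-sided Fisher at 0.05.

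- Sitting: the rejection cutoff is one sitter, since 1 − 0.999^10 = 0.0100 and 1 − 0.999^11 = 0.0109. Power at n = 10 is 1 − 0.7^10 = 97.2% and 1 − 0.6^10 = 99.4%; at n = 11 it is 98.0% and 99.6%. The plan states above 90%.
- Survival, by full enumeration of the Fisher test: 81.9% at n = 10 and 85.9% at n = 11. The plan states above 80%.

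The problem is therefore the population definition, not the power calculation.

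**2. Who is in the set.** A treated patient either reaches 14 or 18 months (first limb) or stops earlier. Stopping earlier through death, an AE, non-compliance, consent withdrawal or investigator discretion leads into the second limb. Almost no treated patient falls outside both. Section 7.2 allows up to 20 patients to obtain at least 15 in ITT, so up to 20 − 15 = 5 (25%) can be non-ITT.

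**3. The cutoff in that set.** With 15 patients, 1 − 0.999^15 = 0.0149. With 20 patients, 1 − 0.999^20 = 0.0198. Both are below 0.025, so one sitter rejects in either set. Hence 0 of 15 ITT sitters plus one sitter among five non-ITT patients fails the ITT test and passes the sensitivity test. This step needs no assumption about untreated rates.

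**4. False rejection through case mix.** Let the 15 ITT patients sit at 0.1%, and m non-ITT patients at an untreated rate q, with no treatment effect. Then

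P(at least one sitter) = 1 − 0.999^15 × (1 − q)^m, where 0.999^15 = 0.9851.

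The protocol gives no q for the non-ITT groups, so q is an assumption shown as a range:

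| q | m = 1 | m = 5 |
|---|---|---|
| 0.1% | 1.6% | 2.0% |
| 3% | 4.4% | 15.4% |
| 5% | 6.4% | 23.8% |
| 10% | 11.3% | 41.8% |

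For example, q = 3% and m = 5 gives 1 − 0.9851 × 0.8587 = 0.154.

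**5. Survival can move either way.** Take 7 of 26 controls surviving (27%, near the planned 25%) as an illustration, with the two-sided Fisher test:

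- ITT 8/15 gives p = 0.108. Adding five surviving non-ITT patients (13/20) gives p = 0.016.
- ITT 10/15 gives p = 0.021. Adding five non-ITT failures (10/20) gives p = 0.133.

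**The case against.** The strongest reply is that nothing confirmatory depends on this analysis. Section 14.3.1 makes ITT primary, and section 14.3.2 places the sequential testing on ITT. A reader might infer that the trial's type I error is inflated; it is not. The completers analysis has no alpha and no gate. This stands, and it limits the point to a misleading supportive analysis.

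The second reply concerns size. A reader might push q up to 50% for all five non-ITT patients and report false rejection near 97%. The protocol does not support that. Enrollment requires SMA Type 1, and Table 4 gives its maximum motor function as never sitting. Section 5.2 calls two SMN2 copies 97% predictive of Type 1, which suggests about 3% or less for pre-symptomatic two-copy infants. It also reports that one-copy patients lived less than 11 months. Only modifier carriers could plausibly have a high rate, and five is the maximum number of non-ITT patients. This also stands, so the low end of the table is the better guide.

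Three further inferences go beyond the text:
- That literally every treated patient qualifies. A patient lost without a listed reason could fall outside, although investigator discretion and non-compliance leave little room for that.
- That this is the only sensitivity analysis. It is the only one the protocol states; the SAP is not at hand and may add others.
- That the controls ignore genotype. Section 14.2 mentions only age and gender matching, but section 14.1.1 says they were chosen for comparability to the target population, and their genotypes are not shown.

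One might also say that completers are implicitly nested in ITT. The text does not support this: section 14.3.1 names the two as separate populations, and section 14.1.2.1 shows that the protocol writes a genotype restriction when it intends one.

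**Conclusion.** The point holds as a stated definition that contradicts sections 14.1.2.3 and 14.2 and applies the 0.1% null to patients for whom it was not argued. The ITT primary analysis, its hierarchy and its power are untouched.

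The firm result is the one-sitter cutoff: a single non-ITT sitter makes the sensitivity test significant even with no ITT sitter. The false-rejection figures depend on the assumed q and on how many non-ITT patients enroll. At 3% they are 4.4% with one such patient and 15% with five, against 1.5% for 15 ITT patients alone. At 10% they are 11% and 42%. The direction is not fixed: pre-symptomatic or modifier patients may raise the result, and one-copy patients may lower survival. The change should be made. Confidence is high on the contradiction and lower on the size.

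**What to change.** In section 14.1.2.2, insert the words *in the ITT population* after the opening words of each limb, so that both limbs draw only on treated ITT patients.

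Keep the discontinuation limb. Deleting it and retaining only observed assessments plus deaths or permanent ventilation would drop ITT patients who withdrew, were non-compliant or left for an AE. That approaches a complete-case analysis, which is favorable if those patients were doing poorly.

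Add to section 14.3.2 that, in this sensitivity analysis, ITT patients who discontinue, die or reach permanent ventilation before the endpoint age without the observed outcome count as failures. Once the set is essentially ITT again, this counting rule is what makes the analysis a test of dropout.

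Report non-ITT and all-treated results only descriptively, as sections 14.1.2.3 and 14.2 already provide, and carry the same wording into the SAP. The cost is a few lines of text, with no added patients, visits or data.

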##### 14.1.2.3. All Enrolled Population

The all enrolled population will consist of all patients who receive an IV infusion of AVXS-101. Analyses of endpoints in this population are considered descriptive.

#### 14.1.2.4. Safety Population

The safety analysis population will consist of all patients who receive an IV infusion of AVXS-101. All safety analyses will be conducted on the safety analysis population.

### 14.2. Sample Size Calculation

This is a pivotal Phase 3, open-label, single-arm, single-dose, study assessing the efficacy and safety of AVXS-101 (gene replacement therapy) in up to twenty (20) patients with spinal muscular atrophy (SMA) Type 1 who meet enrollment criteria, may be either symptomatic or pre-symptomatic and are genetically defined by no functional survival motor neuron 1 gene (*SMN1*) with 1 or 2 copies of survival motor neuron 2 gene (*SMN2*) and who are < 6 months (< 180 days) of age **at the time** of gene replacement therapy (Day 1). Enrolling up to twenty (20) patients under the broader enrollment criteria is projected to enable enrollment of at least 15 patients that meet the Intent-to-Treat Population (ITT) criteria. The ITT population is identified as symptomatic patients with bi-allelic *SMN1* deletions and 2 copies of *SMN2* without the *SMN2* gene modifier mutation (c.859G>C) and will comprise the primary population for evaluation of the primary and secondary endpoints. Study power is based upon efficacy analysis of the ITT population. Furthermore, the first 3 patients enrolled must meet criteria for the Intent-To-Treat Population to enable a comparison of CHOP-INTEND scores at 1-month following gene replacement therapy to enable a comparison of patient response between AVXS-101-CL-303 patients and Cohort 2 patient results from the Phase 1 trial (AVXS-101-CL-101). Patients with 1 copy of *SMN2*, pre-symptomatic patients and patients with the *SMN2* gene modifier mutation (c.859G>C) and other permutations outside of those specified in the ITT population will be evaluated separately as part of additional subgroup analyses. Details of all analyses will be contained within the Statistical Analysis Plan.

The 2 co-primary efficacy endpoints will be assessed in sequence: The endpoint of functional independent sitting will be assessed first and, only if this assessment meets statistical significance will the endpoint of survival be assessed.

Based upon the widely cited natural history of the disease (Pediatric Neuromuscular Clinical Research Network [PNCr]) [*Neurol.* 2014; 83(9):810-817], it is expected that no patients in this population would be expected to attain the ability to sit without support or accomplish other milestones (rolling over, standing, walking) prior to 18 months of age. Assuming that the true response rate for the primary endpoint is actually zero (or as low as 0.1%) in the population of interest of the historical control, the first co-primary efficacy endpoint hypothesis:

$$\begin{aligned} H_0: p_{AVXS-101} &= 0.1\% \\ &\textit{versus the alternative} \\ H_a: p_{AVXS-101} &> 0.1\%, \end{aligned}$$

where  $p$  is the proportion of functional independent sitting for at least 30 seconds at the 18 months of age study visit.

Based upon preliminary results from the ongoing Phase 1 clinical study AVXS-101-CL-101, at least 40% of treated symptomatic patients with bi-allelic deletions of *SMN1* and 2 copies of *SMN2* without the *SMN2* gene modifier mutation (c.859G>C) are expected to achieve the co-primary efficacy endpoint of functional independent sitting for at least 30 seconds at the 18 months of age study visit. With the assumption for the true response rate of AVXS-101 for

the primary endpoint being in the range of 30% - 40%, a sample size of 15 patients that meet ITT criteria will be enrolled and assuming approximately 30% of patients are excluded from analysis, would yield an ITT population that would provide power of > 90% to detect a significant difference from 0.1% with  $\alpha = 0.025$  using a 1-sided exact test for a binomial proportion.

The second co-primary efficacy endpoint hypothesis:

$$H_0: p_{AVXS-101} = p_{HISTORICAL-FINKEL}$$

*versus the alternative*

$$H_a: p_{AVXS-101} \neq p_{HISTORICAL-FINKEL}$$

where  $p$  is the proportion of patients surviving at 14 months of age.

Based upon preliminary results from the ongoing Phase 1 clinical study AVXS-101-CL-101, at least 80% of treated symptomatic patients with biallelic- *SMN1* deletions and 2 copies of *SMN2* without the *SMN2* gene modifier mutation (c.859G>C) are expected to achieve the co-primary efficacy endpoint of survival through 14 months of age. It is anticipated that 75% of patients in the PNCR population would not survive beyond 13.6 months of age, and that these control patients will represent a 25% survival rate based upon the natural history of the disease. With this efficacy, an enrolled sample size of 15 patients that meet ITT criteria (assuming 30% of patients are excluded from the analysis) would yield an ITT population that would provide power of > 80% to detect a significant difference from the historical control with  $\alpha = 0.05$  using a 2-sided Fisher's Exact test, comparing to the 26 age and gender matched patients from a published natural history observational study performed at 3 large, tertiary care centers in the United States (Harvard University, Columbia University, Children's Hospital of Philadelphia; PNCR).

